**Statistical And Analytic Plan**

Demographic and clinical characteristics will be described using summary statistics, including means, standard deviations, medians, and ranges for continuous variables, and frequencies for categorical variables. Analyses will be conducted using Stata 17 (StataCorp, College Station, TX). Raw actigraphy data will be processed using GGIR, a package in R: A language and environment for statistical computing (R Corp Team, Vienna, Austria). The significance level for two-sided hypothesis testing will be set at 0.05.

To assess completeness of CGM data, the number of days with adequate CGM data will be divided by 9, omitting the first 24 hours due to possible inconsistent measurements after initial placement. Feasibility will be defined as  $\geq 80\%$  (7.2) of days with data. To assess completeness of glucose and mixed-meal challenge documentation, the number of participants who document the date and time of glucose and mixed-meal ingestion (including mixed-meal content) will be determined and divided by the total number of participants (40). Feasibility will be defined as  $\geq 80\%$  of participants documenting date and time of either the glucose challenge, mixed-meal challenge, or both. To evaluate test performance characteristics, sensitivity, specificity, and positive and negative predictive values of glucose on CGM 2 hours after at-home glucose beverage ingestion (CGM-2h) to predict OGTT-2h $\geq 140$  mg/dL will be assessed for various thresholds of CGM-2h. Area under the receiver operating characteristic curve (AUC) will be determined. An AUC threshold of  $\geq 0.7$  will be used to define adequate discrimination. Acceptability will be rated on a Likert scale (1: completely unacceptable, 2: mostly unacceptable, 3: neutral, 4: mostly acceptable, 5: completely acceptable). Acceptability will be defined as a mean score for all participants of  $\geq 3$ . Interview transcripts will be reviewed by study staff trained in qualitative analysis. Content analysis will be used to identify themes and sub-themes.

---

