## **6.2 Efficacy Evaluations**

CGM data completeness (data available for  $\geq 80\%$  requested days worn), nutrition logging quality and completion ( $\geq 80\%$  of participants documenting date and time of glucose challenge, mixed meal challenge, or both), and acceptability (mean score  $\geq 3$ , or “neutral” for all participants) will be used to determine feasibility and acceptability of this approach.

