## 7 STATISTICAL CONSIDERATIONS

### 7.1 Primary Endpoint

We will determine the completeness of CGM data capture and adequacy of nutrition logs for evaluation of at-home glucose challenge.

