### 7.4 Statistical Methods

#### 7.4.1 Analysis of Primary and Secondary Outcomes of Interest

Primary objective: Determine the feasibility of at-home, CGM-based glycemia evaluation as measured by adequacy of CGM data capture and nutrition logging quality and completion on days of at-home glucose and mixed-meal challenge.

*H1a: Complete CGM data will be available for  $\geq 80\%$  of requested days worn:* The number of days with adequate CGM data will be divided by 9, omitting the first 24 hours due to possible inconsistent measurements after initial placement. Feasibility will be defined as  $\geq 80\%$  (7.2) of days with data.

*H1b: Documentation of glucose and mixed-meal challenge will be complete and adequate for analysis for  $\geq 80\%$  of participants:* The number of participants who document the date and time of glucose and mixed-meal ingestion (including mixed-meal content) will be determined and divided by the total number of participants. Feasibility will be defined as  $\geq 80\%$  of participants documenting date and time of either the glucose challenge, mixed-meal challenge, or both.

Secondary objective: Determine the test performance characteristics of at-home, CGM-measured glucose challenge with laboratory-based 2-hour OGTT.

*H2: CGM-measured glucose 2 hours and 5 minutes after standardized glucose ingestion will have adequate discrimination of normal ( $<140$  mg/dL) versus dysglycemic ( $\geq 140$  mg/dL) 2-hour OGTT glucose, as assessed by area under the receiver operating characteristic curve  $\geq 0.7$ :* Using participant logs via text message survey or paper-based logs, date and time of home glucose challenge will be determined and labeled in CGM data. A time point 2 hours and 5

---

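### H1b is headed and counted as documentation of both challenges but judged on either one, so the primary logging criterion can be met with no glucose-challenge logs

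*Combined protocol and SAP*

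**What the plan says.** Section 7.4.1 states H1b in three parts that do not match.

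- **Heading:** "Documentation of glucose and mixed-meal challenge will be complete and adequate for analysis for" at least 80% of participants.
- **Numerator:** "participants who document the date and time of glucose and mixed-meal ingestion (including mixed-meal content"), divided by all participants.
- **Decision sentence:** at least 80% "of participants documenting date and time of either the glucose challenge, mixed-meal challenge, or both".

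The Statistical And Analytic Plan in the synopsis pairs the same joint numerator, over a denominator of 40, with the same either-rule. Section 6.2 gives only the either-rule: "of participants documenting date and time of glucose challenge, mixed meal challenge, or both".

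The statements of purpose vary. Section 7.1 defines this part of the primary endpoint as "adequacy of nutrition logs for evaluation of at-home glucose challenge". The abstract and the synopsis objective also tie logging to the glucose challenge. The objective restated above H1a in section 7.4.1 covers both: "nutrition logging quality and completion on days of at-home glucose and mixed-meal challenge". Section 3.1 names no challenge.

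Section 4.1.3 makes the glucose challenge the main comparison with the OGTT. H2 relies on participant logs, from which the "date and time of home glucose challenge will be determined and labeled in CGM data". Section 7.4.3 places mixed-meal test performance among the exploratory analyses.

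**The concern.** The quantity counted is not the quantity judged. Between the numerator and the decision sentence, the joint requirement becomes an either-requirement, and the conditions on meal content and adequacy for analysis disappear.

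The rule that remains does not measure the endpoint. A meal-only log says nothing about whether the at-home glucose challenge can be evaluated, and without a glucose time the 2 h 05 min CGM value for H2 cannot be located. Yet that participant scores the same as one who logged the glucose challenge in full. H1a does not fill the gap, because it counts days of CGM data. The 32 evaluable subjects in section 7.5 are a planning assumption, not a criterion for glucose logs.

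What is at stake is the primary verdict. The same logs could be called feasible or not feasible depending on which sentence is applied, and the plan leaves that choice open until the logs have been seen.

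**Working it through.** **Inputs from the documents.** Threshold 80% (7.4.1, 6.2, synopsis). Denominator 40 (synopsis; section 4.2.2 makes 40 a maximum). Pass count: 0.80 × 40 = 32. Section 7.5 also arrives at 32, as 40 × (1 − 0.20); this reproduces but is a different quantity.

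**What the either-rule permits.** It passes at 32 participants whatever the mix: 0 glucose logs + 32 meal-only; 16 + 16; or 24 + 8. In the last case glucose logging is 24/40 = 60%.

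**Assumptions.** The documents give no logging rates. Let *g* and *m* be the probabilities of logging the glucose and the meal challenge, and φ the correlation between the two. The same participants answer the same three daily surveys (sections 5.3.1 to 5.3.3), so positive correlation is plausible and independence (φ = 0) is treated as the upper bound.

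**Formulas.**
- P(both) = g·m + φ·√[g(1−g)m(1−m)]
- P(either) = g + m − P(both)
- P(pass) = P(X ≥ 32), X binomial with n = 40

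Everyone counted under a glucose-required rule is also counted under the either-rule. The probability that the either-rule passes while the glucose rule fails is therefore the difference of the two pass probabilities.

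*Worked case*, g = m = 0.80, φ = 0.5: P(both) = 0.64 + 0.5 × 0.16 = 0.72; P(either) = 1.60 − 0.72 = 0.88; P(pass) = 0.956 under the either-rule and 0.593 under the glucose rule; difference 0.363.

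Four entries in a cell are for φ = 0, 0.5, 0.7, 1:

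| Rate for each challenge | P(pass), either-rule | P(pass), glucose required | Either passes, glucose fails |
|---|---|---|---|
| 70% | 0.99, 0.62, 0.37, 0.11 | 0.11 | 0.88, 0.51, 0.26, 0 |
| 80% | >0.999, 0.96, 0.86, 0.59 | 0.59 | 0.41, 0.36, 0.26, 0 |
| 85% | >0.999, 0.99, 0.97, 0.86 | 0.86 | 0.14, 0.13, 0.11, 0 |
| 90% | >0.999, >0.999, 0.998, 0.985 | 0.985 | 0.016, 0.015, 0.014, 0 |

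**Unequal rates.** The disagreement vanishes at complete overlap only because the two rates are set equal. If 60% log the glucose challenge, 90% log the meal, and every glucose logger also logs the meal, then P(either) = 0.90. The either-rule passes with probability 0.9845 and the glucose rule with 0.0061, a difference of 0.978.

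**The case against.** The either-rule appears three times and is the only sentence that defines feasibility, so it looks deliberate. The heading could be read as a hypothesis, and the numerator as a separate count for each challenge with no threshold attached. The objective restated in section 7.4.1 names both challenges, so the rule might be meant to test whether families can log any timed home challenge. The plan could then be made consistent by rewording the heading and numerator to match. Further, the largest probabilities need independence. With equal rates and correlated logging the disagreement also fades at low rates: at 60% each it is 0.17 (φ = 0.5) or 0.05 (φ = 0.7). Finally, this is a single-site pilot, and the times and meal details are collected separately, so every version can be tabulated later.

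Part of this stands. No data are lost, H2 will show its own number of participants, and the probabilities are illustrations. But repetition does not reconcile the rule with its own heading or with section 7.1. Even if the numerator means separate counts, the decision sentence pools them and a meal-only participant still passes. Matching the heading to the either-rule would leave a criterion that can be met with no evidence on the stated endpoint. The fading at low rates depends on equal rates; low glucose logging with high meal logging gives a wrong verdict at any overlap.

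**Conclusion.** The concern holds and needs correcting, because it affects a primary pass criterion. The contradiction and the missing minimum for glucose logs are plain from the text and rest on no assumption.

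The size does rest on assumptions. With equal logging rates of 70% to 80% and φ between 0.5 and 0.7, the chance of a feasible verdict that a glucose-required rule would not give is 0.26 to 0.51. It is zero under complete overlap and at most 0.016 once both rates reach 90%. If glucose logging lags well behind meal logging, it can approach certainty. The case of 32 meal-only logs shows what the rule allows, not what is likely.

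**What to change.** Make heading, numerator and decision rule agree in the synopsis, section 6.2 and section 7.4.1, so that a participant counts only if the glucose challenge is documented. Two versions have support in the text, and the sponsor should choose one.

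- **(a) Follow H1b's heading and numerator:** *H1b is met if at least 80% of all enrolled participants record the date and time of both challenges, with the content of the mixed meal.*
- **(b) Follow section 7.1:** *H1b is met if at least 80% of all enrolled participants record the date and time of the glucose challenge well enough for CGM-2h to be located.* The heading and numerator are then cut to the glucose challenge.

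State the rule as a percentage of all enrolled, since 40 is a maximum. Align the objective in the abstract, synopsis, section 3.1 and section 7.4.1 with the choice, and section 7.1 as well under (a).

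Under either version, report as proportions of all enrolled, with exact 95% confidence intervals: glucose documented; mixed meal with content; both; and glucose documented with usable CGM values at ingestion and at 2 h 05 min. For scale, 32/40 has a Clopper-Pearson interval of 0.644 to 0.909.

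**Cost.** Text changes only; sections 5.3.2 and 5.3.3 already collect the data. Because this replaces a primary criterion, it should be dated before the logs are tabulated, and reported as post hoc if they already have been. The bar becomes harder to meet. Under (b), P(pass) is 0.59, 0.86 and 0.98 at true rates of 80%, 85% and 90%. Under (a), for φ = 0, 0.5, 0.7 and 1, it is 0.02, 0.17, 0.31 and 0.59 at 80% each, and 0.65, 0.88, 0.94 and 0.98 at 90% each.

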### 6.1.6 Interview and Disordered Eating Questionnaire

Semi-structured individual interviews will be conducted by study staff after the observation period to evaluate acceptability of use of CGM for diabetes risk assessment, including barriers and facilitators to this approach. Interviews will be audiorecorded and then professionally transcribed for qualitative analysis using NVivo software.

The disordered eating questionnaire includes 12 questions that inquire about the feeling of “loss of control” when eating. This questionnaire does not have a validated threshold for normal versus abnormal and is not in clinical use in its form in this study.

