minutes later (accounting for lag due to interstitial measurement)(Wadwa, Laffel et al. 2018) (CGM-2h) will serve as the comparison to the 2-hour glucose during OGTT obtained at the study visit (OGTT-2h). Sensitivity, specificity, and positive and negative predictive values of CGM-2h to predict OGTT-2h $\geq$ 140 mg/dL will be assessed for various thresholds of CGM-2h. Area under the receiver operating characteristic curve (AUC) will be determined. An AUC threshold of  $\geq$ 0.7 will be used to define adequate discrimination. The same analysis will be repeated for the comparison of baseline CGM glucose (at time of glucose ingestion) to fasting glucose on OGTT, using a fasting glucose threshold of  $\geq$ 100 mg/dL to define dysglycemia. Finally, correlation analyses (Spearman or Pearson depending on distribution) will be performed to further explore the relationship between CGM indices obtained during at-home glucose challenge (e.g., baseline, peak, mean glucose) and both laboratory-measured HbA1c and plasma glucose during OGTT. Correlations will be examined across subgroups such as lower versus higher ActiGraph-measured physical activity level and self-reported carbohydrate intake on the day prior to at-home glucose challenge, age, pubertal stage, and body mass index.

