#### 7.4.3 Exploratory analyses

The analyses for at-home glucose challenge described above will be repeated to evaluate the test performance of at-home mixed-meal challenge in comparison to 2-hour OGTT. In addition, CGM metrics such as average, area under the curve, and peak glucose as well as coefficient of variation will be compared for days of CGM wear without glucose or mixed-meal challenge versus challenge days to assess the difference in glucose trends of typical daily life versus those artificially imposed by testing.

An additional exploratory analysis will use responses from the disordered eating questionnaire to assess whether correlations between OGTT and CGM-measured glycemia differ between youth with higher versus lower self-report of loss-of-control eating.

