### **7.5 Sample Size and Power**

The sample size for this pilot study balances feasibility with the likelihood of obtaining meaningful results for future studies. Assuming 20% drop-out or incomplete data, a sample size of 40 should lead to 32 evaluable subjects. This will allow for subgroup analyses, including by sex and physical activity strata (high versus low). This study will include nearly twice as many participants with known dysglycemia (or more if previously undiagnosed) as those without in order to maximize the ability to compare impaired glucose tolerance and abnormal CGM-measured glucose trends.

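### Effect modification is judged by comparing subgroup correlations, some on higher/lower splits without a stated cut-point; this loses information and can mistake unequal glucose spread for unequal agreement

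*Combined protocol and SAP*

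**What the plan says.** Section 7.4.1, after the H2 analysis, states that "correlation analyses (Spearman or Pearson depending on distribution) will be performed to further explore the relationship between CGM indices" from the home challenge and both HbA1c and plasma glucose during the OGTT. It continues: "Correlations will be examined across subgroups such as lower versus higher ActiGraph-measured physical activity level and self-reported carbohydrate intake on the day prior". Age, pubertal stage and body mass index complete the list, with no rule for grouping them. Section 7.3 has age strata (8-14, 15-18), but for recruitment.

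Section 7.4.3 sets a comparative aim for the eating questionnaire, namely to "assess whether correlations between OGTT and CGM-measured glycemia differ between youth with higher versus lower self-report of loss-of-control eating". Section 6.1.6 says of that instrument: "This questionnaire does not have a validated threshold for normal versus abnormal".

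Section 7.5 gives the numbers: "Assuming 20% drop-out or incomplete data, a sample size of 40 should lead to 32 evaluable subjects". It names sex and high/low activity as subgroup analyses which that number permits. The synopsis sets the test level: "The significance level for two-sided hypothesis testing will be set at 0.05".

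The documents give no cut-point for activity, carbohydrate or eating score, no test for a difference between correlations, and no interaction term. The multivariable models in section 7.3 adjust for covariates and name no outcome.

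**The concern.** There are two separate weaknesses.

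First, activity and carbohydrate intake are continuous, and the eating score is at least ordered. Reducing them to two groups discards the ordering within each group. For the eating score any cut must be arbitrary or taken from the data.

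Second, a correlation mixes two things: how closely CGM follows the OGTT, and how widely glucose varies in the group. Enrolment deliberately combines 25 youths with known dysglycemia and 15 at risk. A moderator related to glycemic status could therefore have unequal glucose spread in its two halves. The group with the narrower spread would show the lower correlation even if CGM were equally accurate in both.

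At stake is what this pilot passes on. A lower correlation in one subgroup could be reported as poorer performance of home CGM there and shape the next study, while real moderation would be harder to see.

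**Working it through.** **Inputs.** From the documents: 40 enrolled, 20% loss, two-sided 0.05. Assumed, because the documents give none: an even split, OGTT SDs, CGM error SD (30.6 mg/dL), a CGM-on-OGTT slope of 1, and interaction sizes.

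**1. The plan's figure.** 40 × (1 − 0.20) = 32 evaluable, as stated. An even split gives 16 v 16.

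**2. Information kept by a split.** For a normal moderator cut at proportion p, the share kept is φ(z_p)² / [p(1 − p)]. At the median this is (1/2π)/0.25 = 2/π = 0.637. The loss is 36.3%, and 32 × 0.637 ≈ 20 effective subjects. A 1/3:2/3 cut loses 40.5%; a 1/4:3/4 cut loses 46.1%. These figures do not transfer to Tanner stage.

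**3. Spread alone moves r.** With slope 1, r = S / √(S² + 30.6²), where S is the OGTT SD.
- S = 30: r = 0.70
- S = 20: r = 0.55
- S = 15: r = 0.44

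**4. False differences at 16 v 16.** The Fisher-z standard error is √(1/13 + 1/13) = 0.392.
- SD 30 v 15: atanh(0.70) − atanh(0.44) = 0.867 − 0.472 = 0.395, about 1.01 standard errors. The rejection probability is about 17%; simulation gives about 18%.
- SD 30 v 20: 0.867 − 0.614 = 0.253, about 0.65 standard errors. The rejection probability is about 10%, and simulation agrees.
- Equal spread: about 5%.

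The interaction of OGTT glucose with group, with CGM as outcome, rejects about 5% in all three cases when OGTT glucose is free of error.

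**5. Power for a real interaction (simulation, n = 32).** With y = 0.6·o + 0.4·o·m + 0.8·e, where o, m and e are standard normal, power is about 63% for the continuous interaction and about 37% for split-half correlations. With the coefficient 0.4 reduced to 0.2 it is 23% v 12%.

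**6. What the interaction misses.** Take equal slopes and OGTT SD 30 in both groups, but CGM error SD 15 v 45. The true correlations are 30/√(900 + 225) = 0.89 and 30/√(900 + 2025) = 0.55. The correlation comparison rejects about 55-57% of the time, the interaction about 6%. At error SD 20 v 40 it is about 26% v 5%. Separately, with an OGTT error SD of 20 mg/dL the interaction rejects falsely about 11% of the time (SD 30 v 15) and 18% (SD 40 v 15).

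**7. The CGM-minus-OGTT difference.** With slope b, its SD is √[(b − 1)²S² + σ²]. At b = 1 this is σ whatever the spread, and regressing the signed or absolute difference on the moderator kept about 5% false rejection under unequal spread. At an assumed b = 0.6, the SDs for S = 30 and 15 are √(144 + 936) = 32.9 and √(36 + 936) = 31.2, so little of the artefact returns.

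**8. Precision.** 80% power needs a Fisher-z difference of (1.96 + 0.84) × 0.392 = 1.10. Against r = 0.5 in one group, the other would need r of about 0.93 or −0.50.

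**The case against.** The strongest objection is to the obvious remedy. A reader might infer that a regression interaction cures both weaknesses and should replace the correlations. Neither the documents nor the calculations support that. Section 2.3 frames the loss-of-control question as a larger discrepancy between home and laboratory glycemia, and an interaction slope does not measure the size of a discrepancy (step 6). It also rejects too often once OGTT error is allowed for. This objection stands and determines the fix.

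A reader might also infer that every moderator is split in two at its median, or that section 7.4.1 plans a significance test between subgroups. The text does not say so. The split is explicit only for activity, carbohydrate and loss-of-control eating. No median is mentioned. Section 7.4.1 only examines correlations across subgroups, and only section 7.4.3 asks whether they differ, without naming a test. The rejection rates above belong to an assumed Fisher-z test on Pearson correlations with normal data; the plan also allows Spearman.

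The size depends on the inputs. The documents do not support any particular SD ratio, and the enrichment is by dysglycemia status, which is not one of these moderators. At more moderate ratios and weaker interactions, the excess of false differences and the gain in power both shrink.

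What survives is the direction of both effects and the lack of any threshold for the eating score.

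**Conclusion.** The point holds as a minor one. Splitting a roughly normal moderator at its median costs about 36% of the information, and uneven cuts cost more. Comparing correlations can produce differences from spread alone: about 18% false rejection at an assumed two-fold SD ratio and about 10% at 30 v 20 mg/dL, under the test and sample split assumed above. Keeping the moderator continuous raises power (63% v 37% in one favourable scenario) but leaves it modest at 32 evaluable subjects.

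It would be wrong to conclude that the main results are in doubt. Section 7.4.1 describes the correlations as further exploration, section 7.4.3 is headed exploratory, and no decision rule uses them. H1a, H1b, H2 and the acceptability criterion are untouched.

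**What to change.** In sections 7.4.1 and 7.4.3:

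1. Keep activity, carbohydrate intake, age, body mass index and the eating score continuous, and treat Tanner stage as ordinal.
2. For like-for-like pairs (CGM-2h with OGTT-2h, baseline CGM with fasting glucose), regress the signed and the absolute CGM-minus-OGTT difference on the moderator. This speaks directly to discrepancy.
3. For slope differences, regress the CGM value on OGTT glucose, the moderator and their product, with robust standard errors. Keep CGM as the outcome: with CGM as predictor, the slopes in step 3 of the working become 900/(900 + 936) = 0.49 and 225/(225 + 936) = 0.19 with no real moderation, and simulated false rejection was 36%. For indices without a laboratory counterpart, such as peak or mean glucose against HbA1c, only this interaction model applies.
4. Report estimates with 95% confidence intervals rather than verdicts of significance.
5. Keep subgroup correlations as description only, each shown with its group's glucose SD, and do not read them as differences in accuracy.

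The cost is SAP wording; data and software stay the same. The drawbacks should be stated in the plan: approximate linearity is assumed and should be checked by plot; the interaction is not immune to OGTT measurement error and cannot detect differences in error size; the difference analysis is cleanest when the slope is near 1; and intervals will be wide at this sample size.
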